Potential genetic determinants of treatment response will be examined by the assessment of genetic variants in relation to treatment outcome. A blood sample will be obtained from patients who have signed a separate informed consent form for the pharmacogenomic analyses. The blood sample can be obtained at any visit post Screening, and the patient has agreed to be tested and has signed the separate informed consent form; i.e., the blood draw is not tied to any specific study visit, hence it can be obtained at any time post Screening. But due to circumstances caused by the COVID-19 pandemic and possibility of no further in-clinic visits after Baseline visit (Visit 2), it is strongly recommended that the pharmacogenomics blood sample be obtained at the Baseline visit (Visit 2).

The first step of the pharmacogenomic analyses will involve exome sequencing and analysis for allelic polymorphisms related to treatment response to TNX-102 SL. It is presumed that unused sample will be stored up to fifteen years, and potentially utilized to develop a pharmacogenomic test for determining likelihood of treatment response to TNX-102 SL.

Table 2: Study Design and Schedule of Assessments

Assessment	Screening and Washout Period ^a	Run-In Period (Diary for Symptoms)	Baseline/Randomization	Week 2 ^r	Week 6 ^r	Week 10 ^r	Week 14/ET ^b
				Day 15 -4 /+7 days	Day 43 ± 7 days	Day 71 ± 7 days	Day 99 -4 /+7 days
Study Day	Day -35 to -1	Day -7 to -1	Day 1				
Visit Number	1		2	3	4	5	6
Informed consent	X						
Inclusion/exclusion criteria	X						
Demographics	X						
Medical history	X		X ^k				
Prior/Concomitant medications	X		X ^k	X	X	X	X
Lifetime FM pharmacotherapy history	X						
Physical examination	X		X ^c				X
Inspection of oral cavity ⁿ	X		X	X	X	X	X
2016 Revision to 2010/2011 FM Diagnostic Criteria	X						
MINI 7.0.2 Modules A, C, I, J, K (MDE, Bipolar, EtOH, Substance Use, Psychotic Disorders)	X						
MSI-BPD	X						
Columbia-Suicide Severity Rating Scale (C-SSRS)	X		X	X	X	X	X
Beck Depression Inventory (BDI-II) ^q	X		X	X	X	X	X
In-clinic assessment of pain (24-hour & weekly recall) ^q	X ^p		X	X	X	X	X
FIQR ^q			X	X	X	X	X
PROMIS – Sleep Disturbance ^q			X	X	X	X	X
PROMIS - Fatigue ^q			X	X	X	X	X
PGIC Assessment ^q				X	X	X	X
CSFQ-14 (female or male version, as appropriate) ^q			X				X

Assessment	Screening and Washout Period ^a	Run-In Period (Diary for Symptoms)	Baseline/Randomization	Week 2 ^r	Week 6 ^r	Week 10 ^r	Week 14/ET ^b

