^{*/*} The blood draw for the pharmacogenomic assessment can be obtained at any study visit post-Screening (including an Early Termination visit). Due to circumstances caused by the COVID-19 pandemic and possibility of no further in-clinic visits after Baseline visit (Visit 2), it is strongly recommended that the pharmacogenomics blood sample be obtained at the Baseline visit (Visit 2). It should only be obtained one time during the study. Separate written, signed informed consent is required if the patient is to participate in the optional pharmacogenomic assessment.

^P Weekly recall of daily average pain intensity on the NRS scale is required at the Screening Visit. Patients should only continue screening if they score ≥ 4 and ≤ 9 . A score outside this range will require Medical Monitor approval in order to continue in screening.

^Q For telephone visits, the patient will be mailed all the applicable patient reported outcomes for a given visit. The results of the BDI-II will be reviewed with the patient (specifically Question #9 which will allow further exploration of any suicidal thoughts or wishes implied by the patient's self-reported response, if applicable) during the phone call. C-SSRS interview should only be conducted after the BDI-II Question #9 inquiry, as any discrepancy between Question #9 response and C-SSRS suicidal ideation types endorsed for the same assessment period must be resolved to avoid presence of occult suicidal ideation not recognized by site staff.

^r Week 2, Week 6, and the Week 10 visits may be performed via telephone only when an in-clinic visit is not feasible due to the COVID-19 pandemic. Select safety assessments specifically required in-clinic will not be required for the telephone visits (e.g. vital signs and oral cavity exam). Telephone visits for Week 14/ET visits are to be strongly discouraged due to inability to obtain several safety measures (e.g. vital signs, physical exam, oral cavity exam, chemistry and hematology labs), but telephone visits will be permitted for Week 14/ET visit if attendance of an in-clinic visit is absolutely impossible or refused by the patient as a result of the COVID-19 pandemic and it is not feasible for the site to conduct a home visit.

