11.1.4. Screening Assessments and Procedures

The following screening assessments/procedures will be completed in the following general order:

- Obtain written informed consent to participate
- Inclusion/exclusion criteria
- Demographics
- Medical history
- Confirmation that patient satisfies the 2016 Revisions to the 2010/2011 fibromyalgia diagnostic criteria (2010 American College of Rheumatology provisional diagnostic criteria/2011 self-report modification for survey and clinical research)
- Prior medication history
- Lifetime fibromyalgia pharmacotherapy history
- NRS assessment of 7-day recall of average daily pain. Patients should only continue screening if they score ≥ 4 and ≤ 9 . A score outside this range will require Medical Monitor approval in order to continue.
- Mini International Psychiatric Interview 7.0.2 – Modules A (Major Depressive Episode), C (Manic and Hypomanic Disorders), I (Alcohol Use Disorder), J (Substance Use Disorder), and K (Psychotic Disorders)
- MSI-BPD
- BDI-II. Any patient with a BDI-II total score > 24 or a response of 2 or 3 to item #9 (suicidal ideation) is not eligible for randomization.
- “Baseline/Screening” version of the C-SSRS. Any patient with C-SSRS Type 4 or 5 ideation during the preceding 6 months or any suicidal behavior during the preceding 12 months should be screen failed.
 - a. Results of the C-SSRS and BDI-II should be reviewed together at each visit to ensure (1) the patient is not experiencing suicidal ideation or worsening depression that requires intervention and (2) both scales are providing a consistent clinical picture of the patient with regard to suicidality.
- Physical examination, including vital signs, height, weight and BMI. Patients with BMI >45 must receive Medical Monitor approval prior to randomization.
- Thorough examination of the oral cavity. This examination should include a careful visual examination of the sublingual area, tongue, buccal mucosa, lips, palate and gums, aided with a tongue depressor, as well as palpation of the lips, hard palate, and

floor of the mouth. Any abnormalities should be noted on the oral cavity examination source document.

- Clinical laboratory tests
- Drug screening
- Serum pregnancy test (for women of child-bearing potential)
- 12-lead electrocardiogram
- Only those patients meeting all of the inclusion and none of the exclusion criteria will be eligible to continue. Eligible patients will:

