11.2.2. Baseline Visit

For patients who have qualified for randomization, these assessments and procedures will be completed in the following general order:

- Confirm patient's eligibility based on the diary data collected during the preceding 7 days
- Review completed diary data with the patient
- Update medical history (with any changes noted since screening)
- Assess changes in medication history and concomitant medications
- Have the patient complete the BDI-II. If the BDI score is >24 , the patient is not eligible for randomization and should be screen failed. In addition, a score > 1 on item #9 (suicidal ideation) is exclusionary.
- Administer the "Since Last Visit" version of the C-SSRS. Any patient exhibiting Type 3, 4, or 5 suicidal ideation or any suicidal behavior since the Screening visit should be screen-failed and assessed for appropriate follow-up care.
 - a. Results of the C-SSRS and BDI-II should be reviewed together to ensure (1) the patient is not experiencing suicidal ideation or worsening depression that requires intervention and (2) both scales are providing a consistent clinical picture of the patient with regard to suicidality.
- Assess occurrence of adverse events
- Conduct a brief physical examination, including vital signs and weight
- Conduct a visual examination of the oral cavity. This examination should include a careful visual examination of the sublingual area, tongue, buccal mucosa, lips, palate and gums. Any abnormalities should be noted on the oral exam source document. It is recommended that both non-significant as well as significant findings be noted so that there is a complete and accurate baseline assessment available for comparison to findings at later visits.
- Perform urine pregnancy test (for women of child-bearing potential)
- Patient should complete the following patient-reported outcomes (PRO):
 - a. FIQR
 - b. Clinic administered assessment of pain by both 24-hour and weekly recall using 11-point (0-10) NRS scale
 - c. PROMIS scales for sleep disturbance and fatigue
 - d. CSFQ-14 female or male version, as appropriate
- Ensure that all PROs were accurately and fully completed

- Once it has been confirmed that the patient remains eligible, randomize patient via IRT Randomization System
- Dispense bottle of double-blind study drug as assigned via the IRT
- Review patient instructions regarding study drug dosing and diary completion (Section 10.2 and Section 12.2.6).

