13. STATISTICAL CONSIDERATIONS AND ANALYSES

A complete description of the statistical analyses to be performed will be provided in the study-specific SAP, which will be finalized prior to database lock and the unblinding of study treatments.

Baseline will be defined as those values recorded closest to, but prior to administration of the first dose of study drug.

Unless otherwise noted, significance tests of treatment differences will be tested at the two-sided 0.05 level.

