3.2.2 Exploratory Endpoints

Exploratory efficacy endpoints include:

- Proportion of subjects with a $\geq 30\%$ improvement from baseline to Weeks 1-14 in the daily self-reported pain severity score
- Proportion of subjects with a $\geq 50\%$ improvement from baseline to Weeks 1-14 in the daily self-reported average pain severity scores
- Proportion of subjects with a PGIC rating of "very much improved" or "much improved" at all post-randomization clinic visits
- Mean PGIC rating at all post-randomization clinic visits

- Change from baseline in the FIQR total score, overall impact domain score, and individual item scores at all post-randomization clinic visits
- Change from baseline in the FIQR symptoms domain score and function domain scores at all post-randomization clinic visits
- Change from baseline in the PROMIS score for sleep disturbance at all post-randomization clinic visits
- Change from baseline in the PROMIS score for fatigue at all post-randomization clinic visits
- Change from baseline in the weekly average of the daily diary assessment of sleep quality at Weeks 1-14
- Change from baseline in the weekly average of the daily self-reported average pain severity scores at Weeks 1-14
- Changes from baseline in patient-rated Changes in Sexual Functioning Questionnaire Short-Form (CSFQ-14) in females and in males, analyzed separately
- Change from screening in the in-clinic assessment of pain (24-hour & weekly recall)

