8. GENERAL ISSUES FOR STATISTICAL ANALYSIS

8.1 General Statistical Methodology

Descriptive summaries will be provided where appropriate for each of the primary and secondary variables. In general, tables will summarize data by treatment group and visit. All subjects for a population in each treatment group will be grouped together; subjects that reduce dose from two tablets per day to one tablet per day will not be reported separately for the analyses described in this SAP, unless otherwise noted. If there are more than 10 subjects in the active arm with a dose reduction at any point in the study, summary statistics on key outcomes may be reported for subjects with dose reductions.

Baseline characteristic and safety tables will be completed for the Safety Population unless otherwise specified. Efficacy tables will be presented for the ITT Population.

Continuous, quantitative variable summaries will include the number of subjects (N) with non-missing values, mean, standard deviation, median, minimum, and maximum.

Categorical, qualitative variable summaries will include the frequency and percentage of subjects who are in the particular category. In general, the denominator for the percentage calculation will be based upon the total number of subjects in the study population for the treatment group unless otherwise specified.

Baseline values are defined as the last non-missing measurement prior to the first dose of study drug. For scores obtained via diary, baseline will be defined as the average of the scores from the 7 days prior to the baseline visit. Change from baseline will be defined as the post-baseline visit value minus the baseline value.

Study day is defined as assessment date – first dose date +1.

All analyses will be performed using SAS[®] Software version 9.3 or later.

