The CSFQ-14 is completed at baseline and Week 14/ET. It has a male and a female version, which will be analyzed separately. The CSFQ-14 will be analyzed for its total score, three subscales on phases of sexual response, and five subscales for dimensions of sexual functioning by using an Analysis of Covariance (ANCOVA) model. The model will include the fixed, categorical effects of treatment and site, plus a baseline covariate corresponding to the subscale (or total) being analyzed. Significance testing will be based on least-squares means using a two-sided $\alpha=0.05$ test and two-sided 95% confidence intervals will be presented. This outcome is considered to be supportive of the product's safety; other exploratory analyses are for further support of product efficacy.

The FIQR exploratory endpoints and the in-clinic pain assessments will be analyzed using an MMRM including the fixed, categorical effects of treatment, site, study week, and treatment by study week interaction, as well as the fixed covariates of baseline value and baseline value score-

by-study week interaction. An unstructured covariance structure will be used to model the within-subject errors. If this analysis fails to converge, the following structures will be tested in this order: first order ante dependence, heterogeneous first order autoregressive, heterogeneous compound symmetry and compound symmetry with the first to give convergence used. The Kenward-Roger approximation will be used to estimate the denominator degrees of freedom. Note that the screening values will be used as baseline for the in-clinic pain outcomes.

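### The SAP takes Screening as baseline for both in-clinic pain ratings, contrary to its own general rule and without a reason, and the 24-hour rating is probably not collected at Screening

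*SAP*

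**What the plan says.** SAP 3.2.2 lists the exploratory endpoint as "Change from screening in the in-clinic assessment of pain (24-hour & weekly recall", so it covers both recall periods. SAP 10.3 analyses it with a repeated-measures model that includes the baseline value and its interaction with study week, and adds: "Note that the screening values will be used as baseline for the in-clinic pain outcomes".

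The general rules differ. SAP 8.1 states: "Baseline values are defined as the last non-missing measurement prior to the first dose of study drug". Its only separate provision is for diary scores. Protocol 13 states: "Baseline will be defined as those values recorded closest to, but prior to administration of the first dose of study drug".

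On data collection, the Protocol 11.2.2 list for Visit 2 includes "Clinic administered assessment of pain by both 24-hour and weekly recall using 11-point (0-10) NRS scale". The Screening list in Protocol 11.1.4 has only "NRS assessment of 7-day recall of average daily pain". In Protocol Table 2 one row, "In-clinic assessment of pain (24-hour & weekly recall", is marked at Screening with footnote p, and that footnote says: "Weekly recall of daily average pain intensity on the NRS scale is required at the Screening Visit".

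SAP 13 reports that the in-clinic pain assessments had been left out of the protocol's exploratory list by oversight and were added. It does not say why Screening is their baseline.

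**The concern.** There are two separate problems.

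First, the choice departs from the definition used elsewhere in the plan and is not explained. Values that satisfy SAP 8.1 exist at Visit 2 for both ratings, yet the SAP gives them no role. The FIQR exploratory endpoints share the same model description in SAP 10.3. They are first collected at Visit 2, so one specification carries two different baselines.

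Second, a 24-hour rating is probably not taken at Screening. If so, both the change score and the required covariate are missing for every patient, and the sponsor would have to pick a replacement outside the plan.

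For weekly recall the analysis can be run, but its baseline precedes washout in patients who need one. It is also the score used for the 4-to-9 entry criterion (Protocol 8.2, criterion 3, with Medical Monitor exceptions). A within-arm change from that value mixes medication withdrawal and regression to the mean with change on treatment. It also starts at a different point from the primary diary endpoint, whose baseline is the 7 days before Visit 2.

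**Working it through.** The plan states no figure here to reproduce. The main check is a cross-reading, followed by two small calculations.

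**Is 24-hour recall collected at Screening?**

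| Source | What it indicates for Screening |
|---|---|
| Protocol Table 2, row label | Both recalls; Screening cell marked, subject to footnote p |
| Protocol Table 2, footnote p | Weekly recall only |
| Protocol 11.1.4, Screening list | 7-day recall only |
| Protocol 7.1 and 8.2 (criterion 3) | Mention only the 7-day rating |
| Protocol 12.2.4 | Both recalls at Visits 2 to 6; Visit 1 not listed |
| Protocol 11.2.2, 11.3, 11.4, 11.5.1, 11.5.2 | Both recalls named at every later visit and at early termination |

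Protocol 12.2.4 does not settle the point alone, because it also omits the weekly rating that is certainly taken at Screening. The contrast between the Screening list and all later lists, together with footnote p, makes weekly recall only the better-supported reading. The diary cannot fill the gap: it starts on the evening of Visit 1, and Protocol 12.2.4 treats the paper in-clinic rating as a separate measure.

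**How much of the weekly-recall change interval lies before dosing?**

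Inputs: screening period of 7 to 35 days, or 49 with Medical Monitor approval (Protocol 11.1.2); 21 drug-free days before randomization when washout is needed (Protocol 7.1); Visit 6 on Day 99, which is 98 days after Day 1.

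Share = pre-dose days / (pre-dose days + 98):

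- 7 days: 7/105 = 6.7%
- 21 days: 21/119 = 17.6%
- 35 days: 35/133 = 26.3%
- 49 days: 49/147 = 33.3%

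Withdrawal may begin only after consent, so a patient who needs the 21-day washout has at least 17.6%. Protocol 9.1 allows a shorter interval after acute opioid use. With a Visit 2 baseline the share is 0%. These are shares of calendar time, not estimates of bias.

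**What might the older covariate cost in precision?**

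The documents give no correlations, so this is an assumption. Adjusted variance is proportional to 1 − r², where r is the correlation of the baseline with the Week 14 score. Suppose r is 0.1 lower for Screening than for Visit 2:

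- Visit 2 r = 0.4: (1 − 0.3²)/(1 − 0.4²) = 0.91/0.84 = 1.08
- Visit 2 r = 0.5: (1 − 0.4²)/(1 − 0.5²) = 0.84/0.75 = 1.12
- Visit 2 r = 0.6: (1 − 0.5²)/(1 − 0.6²) = 0.75/0.64 = 1.17

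That is 8% to 17% more variance under the assumption, and none if the two correlations are equal.

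**The case against.** The strongest reply is that SAP 3.2.2 and 10.3 agree with each other. A specific rule stated twice normally overrides a general one, so an analyst is not left choosing between two baselines. The endpoint is also openly named as change from Screening. This stands as far as it goes: the choice may be deliberate. It does not supply a reason, and it cannot create a 24-hour rating that was not taken.

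A second reply is that silence in a visit list proves little. Protocol 11 refers to Table 2 for the detailed schedule, the row is marked at Screening, and footnote p does not say that 24-hour recall is omitted. Other visit lists are incomplete too: the dose tolerability assessment is marked at Weeks 6 and 10 in Table 2 but is not an item in the Protocol 11.4 list. The case report form, which would settle the matter, is not among the documents. This is why the conclusion is probable and not certain. Here, however, the Screening list is not silent on pain: it names one recall period where every later list names two.

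A third reply concerns importance. The endpoint is exploratory, SAP 8.1.1.2 makes its p-values descriptive, and washout and regression to the mean affect both arms alike, so the randomized contrast is not biased. Visit 2 is not free of selection either, because the diary criteria in Protocol 8.4 cover the week before it. All of this is accepted and limits the weight of the point.

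**Conclusion.** The concern holds. The Screening baseline departs from SAP 8.1 and Protocol 13 without explanation, although qualifying Visit 2 values are collected for both ratings.

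For 24-hour recall, on the better-supported reading, none of the planned 470 patients has a scheduled Screening value, and the analysis cannot be carried out as specified. This rests on the Screening procedure list and footnote p prevailing over the combined row label.

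For weekly recall, the consequence is interpretive: within-arm change includes a pre-dose period making up about 7% to 26% of the interval to Day 99, or up to 33% with an extended screening period. Some loss of precision is plausible but cannot be quantified from the documents. The between-arm comparison is not biased, and no primary or key secondary result is affected.

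The plan should be corrected, mainly because a prespecified analysis is probably not executable.

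**What to change.** In SAP 3.2.2 and 10.3, take the Visit 2 pre-dose 24-hour and 7-day in-clinic ratings as baseline and model covariate, and rename the endpoint as change from baseline. This agrees with SAP 8.1 and gives a post-washout, pre-dose reference.

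Reconcile the Protocol Table 2 row and its footnote with Protocol 11.1.4 and 12.2.4, stating plainly whether 24-hour recall is collected at Screening. Protocol 12.2.4 should also mention the Screening weekly rating.

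If the sponsor does want a Screening baseline, limit it to weekly recall, give the reason in SAP 13, and say how the Visit 2 value is handled.

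The cost is two SAP sentences and a clarification of the assessment schedule. The Visit 2 data are already being collected.

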10.3.1 Exploratory Analyses of Daily Pain Scores

Randomization Honoring Non-Parametric (RHNP) hypothesis test.

In this exploratory analysis, the primary endpoint of Week 14 change from baseline in daily pain scores will be analyzed by a RHNP method for computing p-values for the hypothesis that treatment has no effect.

Subjects will be randomly reassigned to treatment 10,000 times using the original randomization algorithm, in the order subjects actually enrolled, using the original block sizes and randomization strata. The apparent effect of the treatment under each of these hypothetical assignments will be compared to the apparent effect for the actual assignment, approximating the distribution of the apparent treatment effect under the null hypothesis that treatment makes no difference whatsoever.

The apparent effect size for each random allocation will be quantified by the median difference between the responses of subjects assigned to treatment by that allocation and those assigned to placebo by that allocation.

The test statistic will be calculated for 10,000 random allocations and for the original observed data with actual treatment codes. The percentile rank of the statistic for the true treatment assignment among the distribution of the statistics for the permutations is one-sided p-value for an exact randomized test of the null hypothesis that treatment makes no difference whatsoever. If treatment assignment had no impact, the test statistic for the original observed data would be unlikely to be in the tail of the distribution of values of the test statistic for the random assignments. The percentile is the p-value of the null hypothesis.

The primary test-statistic of interest for the first stage will be the difference in the medians between the treatment and control groups at Week 14. This statistic makes sense for ordinal variables such as the Likert scales that comprise each response. Other test statistics may also be investigated including:

- The difference in treatment means at Week 14
- The LS means from an ANCOVA at Week 14 with covariates for baseline value, site and sex
- The LS means at Week 14 from an MMRM identical to the primary efficacy analysis

In addition to performing the above analyses on the observed data, the randomization test will be repeated using multiple imputation implemented in a manner identical to that described for the primary analysis.

In a third analysis, the RHNP method will handle the missing data by assigning each subject with missing Week 14 values a +10 value for their change; since medians will be utilized, the particular value has no impact as long as it is larger than any possible change and less than 50% of the data are missing. This amounts to assuming that missing responses are “bad” and should be scored as more extreme; the more data are missing, the more it will pull the median in the direction of a finding that treatment is ineffective.

The performance characteristics of the RHNP method will be compared against the parametric approaches described for the primary analyses of the change from baseline to the Week 14 endpoint in the diary NRS weekly average of daily self-reported average pain severity scores.

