4.2 Method of Treatment Assignment and Randomization

The following randomization criteria must be satisfied at the Baseline visit (Visit 2) in order for the subject to continue in the study and be randomized:

1. The subject continues to meet all inclusion and exclusion criteria, including urine and blood test results and is successfully and consistently utilizing the diary system.
2. The subject's FM diary pain ratings satisfy the following criteria, as assessed by diary pain scores (24-hour recall):
 - a. A mean pain intensity score ≥ 4 and ≤ 9 on the 11-point (0-10) NRS scale for the 7 days immediately preceding Visit 2, and
 - b. No more than 2 individual days with a score < 4 on the 7 days immediately preceding Visit 2, and
 - c. No score of 10 on any of the 7 days immediately preceding Visit 2, and
 - d. Pain scores must be recorded on at least 5 out of the 7 days immediately preceding Visit 2.

Before the start of the study, a computer-generated randomization schedule will be prepared. Based on the randomization schedule, eligible subjects will be randomly assigned in a 1:1 ratio to receive TNX-102 SL tablets or placebo tablets for 14 weeks.

Treatment A: For Days 1-14, 1 tablet of TNX-102 SL 2.8 mg taken sublingually (under the tongue) each day at bedtime. For Days 15-98, 2 tablets of TNX-102 SL 2.8 mg (5.6 mg) taken simultaneously and sublingually each day at bedtime.

Treatment B: For Days 1-14, 1 tablet of placebo taken sublingually (under the tongue) each day at bedtime. For Days 15-98, 2 tablets of placebo taken simultaneously and sublingually each day at bedtime.

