6. SAMPLE SIZE DETERMINATION

The study is planned to enroll approximately 470 subjects total in a 1:1 randomization, that is, 235 subjects in each of the TNX-102 SL and placebo arms. [REDACTED]

[REDACTED]

[REDACTED]

The interim analysis will re-evaluate these assumptions and the IDMC may recommend a sample size increase.

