Each week prior to Week 14 will be based on 7-day intervals; depending on the interval selected for "Week 14", this will result in Week 1 having less than 7 days or some "extra" days prior to Week 1. Extra days will be dropped and not included in the analysis; in the case of less than 7 days, the available days will be averaged, as long as there are non-missing values. The earliest

day included in the Week 1 average will be the data entered the day after randomization (covering roughly the 24 hours following their first dose of study drug).

For subjects who withdraw from the study early, that do not have a final study visit or complete the study but do not have data in the 7 days preceding their last visit, the last day of diary data (at or prior to Day 106) will serve as the anchor point for dividing the available data into weeks. First, the nearest nominal end day for a weekly period is identified and this week will be the assigned the data from the 7 days immediately preceding the anchor date. For example, if a subject early terminates on study Day 24, the Week 3 (nominally ending on day 21) average will be based on the 7 days prior to Day 24 (Days 17-23). Lost to follow-up subjects that continue to fill out the diary into Week 14 and beyond will have non-missing values for the Week 14 timepoint for diary outcomes. Day 106 will be the last allowable day to be included in the average.

| Week | Nominal Study Day Intervals |
|----------------------|-----------------------------|
| Baseline | Day -7 to -1 |
| Day of Randomization | Day 1 |
| Week 1 | Day 2 to 7 |
| Week 2 | Day 8 to 14 |
| Week 3 | Day 15 to 21 |
| Week 4 | Day 22 to 28 |
| Week 5 | Day 29 to 35 |
| Week 6 | Day 36 to 42 |
| Week 7 | Day 43 to 49 |
| Week 8 | Day 50 to 56 |
| Week 9 | Day 57 to 63 |
| Week 10 | Day 64 to 70 |
| Week 11 | Day 71 to 77 |
| Week 12 | Day 78 to 84 |
| Week 13 | Day 85 to 91 |
| Week 14 | Day 92 to 98 |

Change from baseline will be defined as the pain score at each week minus the baseline pain score (with baseline and weekly pain scores derived as described above). Thus, negative changes will denote lesser pain and larger negative values will denote greater improvement.

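### SAP 10.3.1 says that scoring missing Week 14 pain as +10 pulls toward an ineffective treatment, but both arms are scored alike, so unequal loss can shift the result either way

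*SAP*

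**What the plan says.** SAP 10.3.1 describes a re-randomization test of the Week 14 change in diary pain. Its lead statistic is "the difference in the medians between the treatment and control groups at Week 14", and the percentile rank among 10,000 re-allocations is a "one-sided p-value for an exact randomized test of the null hypothesis that treatment makes no difference whatsoever".

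A third version of the test handles missing data by "assigning each subject with missing Week 14 values a +10 value for their change". No arm is singled out. The SAP notes that the exact score does not matter "as long as it is larger than any possible change and less than 50% of the data are missing", and then asserts that "the more data are missing, the more it will pull the median in the direction of a finding that treatment is ineffective".

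SAP 8.2.1 fixes the direction of the scale: "negative changes will denote lesser pain and larger negative values will denote greater improvement". A change of +10 is therefore the worst score in whichever arm it falls.

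**The concern.** The sentence about the pull would be right if the statistic were the active-arm median alone. The statistic is a difference. A missing placebo value raises the placebo median by the same mechanism that raises the active median when an active value is missing, so the two pulls oppose each other.

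What is at stake is how a positive result gets read. Apart from the sexual-function questionnaire, SAP 10.3 presents the exploratory analyses as further support for efficacy. A reader who accepts the sentence would take a positive result as having survived a penalty against the drug. If placebo lost more patients, for instance through discontinuation for lack of efficacy (a reason SAP 8.1.3 provides for), the larger penalty would have fallen on placebo.

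**Working it through.** **Inputs from the documents**
- +10 in both arms, difference in medians, one-sided p-value: SAP 10.3.1.
- Negative change is improvement: SAP 8.2.1.
- Entry requires "A mean pain intensity score ≥ 4 and ≤ 9 on the 11-point (0-10) NRS scale" over the 7 days before Visit 2 (SAP 4.2). The largest possible worsening is 10 - 4 = +6, so +10 does exceed any possible change.
- "The study is planned to enroll approximately 470 subjects total in a 1:1 randomization" (SAP 6), that is, 235 per arm.

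**Assumed, because no readable figure is given**
- SD of the Week 14 change: 2.0, range 1.5 to 2.5.
- Missing shares by arm: 0% to 35%.
- One-sided threshold: 0.025.

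The plan gives no figure on this point to reproduce. Its side remark checks out: scoring missing values as 6.5, 10 or 100 gave the same median in a simulated sample with about 20% missing.

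**Step 1: closed form.** If a share m of an arm (m < 0.5) is scored above every observed value, the arm's median becomes the observed quantile at 0.5/(1 - m). For normal data:

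arm median = μ + SD × z(0.5/(1 - m))

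With the same μ and SD in both arms (no pain effect), the difference, drug minus placebo, is

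SD × [z(0.5/(1 - m_drug)) - z(0.5/(1 - m_placebo))].

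The z terms are 0.223 at 15% missing, 0.319 at 20%, 0.431 at 25% and 0.566 at 30%. For 15% v 25%: 2.0 × (0.223 - 0.431) = -0.42.

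| Missing, drug / placebo | SD 1.5 | SD 2.0 | SD 2.5 |
|---|---|---|---|
| 20% / 20% | 0 | 0 | 0 |
| 15% / 20% | -0.14 | -0.19 | -0.24 |
| 15% / 25% | -0.31 | -0.42 | -0.52 |
| 20% / 30% | -0.37 | -0.50 | -0.62 |
| 25% / 15% | +0.31 | +0.42 | +0.52 |
| 30% / 20% | +0.37 | +0.50 | +0.62 |

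Negative values favour the drug.

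**Step 2: the test itself.** Simulation with 235 per arm, SD 2.0, 600 trials of 499 re-allocations, simple 1:1 permutation without centre strata. Monte Carlo error is about 0.6 points at a rate of 2.5% and about 2 points at 30%.

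| Pain effect | Missing, drug / placebo | Mean difference | p ≤ 0.025 for drug |
|---|---|---|---|
| none | 20% / 20% | 0.01 | 2% |
| none | 20% / 25% | -0.23 | 10% |
| none | 15% / 25% | -0.42 | 29% |
| none | 20% / 30% | -0.50 | 31% |
| none | 30% / 20% | +0.49 | 0% |
| 0.5 benefit | 0% / 0% | -0.50 | 58% |
| 0.5 benefit | 20% / 20% | -0.49 | 38% |
| 0.5 benefit | 35% / 35% | -0.52 | 20% |
| 0.5 benefit | 20% / 30% | -1.01 | 85% |
| 0.5 benefit | 30% / 20% | +0.02 | 2% |

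**Step 3: unequal spread.** Take SD 2.2 on drug, 1.8 on placebo and 20% missing on drug. At 23% missing on placebo: 2.2 × 0.319 - 1.8 × 0.384 = +0.01, still marginally against the drug. At 25%: 2.2 × 0.319 - 1.8 × 0.431 = -0.07. The net sign then reverses only once placebo loss passes about 23%.

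**Step 4: would an active-only penalty work?** Suppose +10 goes only to missing active values, missing placebo values get the observed placebo median, and the scoring is re-applied in every re-allocation. The penalty then enters the reference distribution too. With no effect and 20% missing in each arm, the observed statistic averaged +0.62 and the reference +0.64 (200 trials of 199 re-allocations, Monte Carlo error 1 to 3 points), so the p-value gains no conservatism. At 15% v 25% the averages were +0.43 and +0.62, and the test favoured the drug in 11.5% of trials; a separate run gave about 12%. Holding the scores fixed across re-allocations still gave about 7.5%.

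**The case against.** Several things can fairly be said for the SAP.

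- **The sentence is partly right.** When the active arm loses more, the pull is against the drug. With balanced loss, more missing data does make a positive finding less likely (58% to 38% to 20% above). Both stand. They do not support an unconditional statement.
- **The null hypothesis is no difference of any kind, which includes dropout.** Under that strict null the test keeps its level, and excess placebo loss from lack of efficacy would be a real treatment difference. This stands: scoring missing as worst is a legitimate composite. But the sentence does not say that the result mixes pain with retention.
- **Robustness is tested elsewhere.** SAP 10.1.3 has four sensitivity analyses, including all dropouts imputed from the baseline distribution and a tipping-point shift applied to the active arm only. SAP 9.1 tabulates withdrawals and reasons by arm. None of these corrects the sentence, and the withdrawal table does not show Week 14 missingness as such.
- **The p-value is descriptive.** SAP 8.1.1.2 keeps it out of formal inference. That limits the consequence and leaves the misstatement in place.

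A reader might infer that the analysis favours the drug whenever placebo loses more, or that direction depends only on missingness. That goes too far: Step 3 shows that spread also matters, and the documents give no SD by arm. A reader might also infer that the SAP offers this as a formal conservative bound. It never uses that label, and the use it names is comparing the method's performance with the parametric approaches.

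**Conclusion.** The point holds in limited form. The unconditional claim in SAP 10.3.1 is wrong as written, because both arms receive the +10 and the statistic is a difference in medians. With similar spread, balanced loss costs power without shifting the expected difference, and unequal loss shifts it against whichever arm loses more. The size is about -0.42 at 15% active v 25% placebo missing with no pain effect (-0.31 to -0.52 for SD 1.5 to 2.5). In simulation such a null trial gave a one-sided p ≤ 0.025 for the drug about 29% of the time. These sizes rest on assumed dropout rates, SDs, normality and threshold; the direction rests only on similar spread.

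The documents do not support reading this as a threat to the trial's conclusions. The analysis is exploratory and outside the testing hierarchy, and the primary analysis does not use it. They also do not show that placebo will lose more patients; either arm could.

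**What to change.** In SAP 10.3.1:

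1. Delete the clause saying that missing data pulls toward an ineffective treatment.
2. State that missing values are scored alike in both arms, so the arm with more missing data is penalised, and that with unequal dropout the result reflects pain and retention together.
3. Report the percentage with a missing Week 14 value by arm, ideally by reason, beside the result.

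Do not add an active-only +10 version as a re-randomization test, since Step 4 shows that its p-value still rewards excess placebo loss. If it is shown at all, give it as a point estimate only.

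The cost is two or three sentences of SAP text and one line in a table. No new data, no change to the primary analysis and no extra run are needed. A positive result would look less reassuring if placebo loss turns out higher.
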